By studying the addition of laparoscopic (including robotic) Burch colposuspension to laparoscopic sacrocolpopexy, we anticipate optimizing surgical outcomes and minimizing complications for patients.

REFERENCES:

- 1. Wu, J.M., et al., Lifetime risk of stress urinary incontinence or pelvic organ prolapse surgery. Obstet Gynecol, 2014. 123(6): p. 1201-6.
- 2. Brubaker, L., et al., Abdominal sacrocolpopexy with Burch colposuspension to reduce urinary stress incontinence. N Engl J Med, 2006. **354**(15): p. 1557-66.
- 3. Wei, J.T., et al., A midurethral sling to reduce incontinence after vaginal prolapse repair. N Engl J Med, 2012. 366(25): p. 2358-67.
- 4. Geller, E.J., et al., Short-term outcomes of robotic sacrocolpopexy compared with abdominal sacrocolpopexy. Obstet Gynecol, 2008. 112(6): p. 1201-6.
- 5. Hsiao, K.C., et al., Comparison of laparoscopic and abdominal sacrocolpopexy for the treatment of vaginal vault prolapse. J Endourol, 2007. 21(8): p. 926-30.
- 6. Klauschie, J.L., et al., A comparison of laparoscopic and abdominal sacral colpopexy: objective outcome and perioperative differences. Int Urogynecol J Pelvic Floor Dysfunct, 2009. **20**(3): p. 273-9.
- 7. Paraiso, M.F., et al., Laparoscopic and abdominal sacral colpopexies: a comparative cohort study. Am J Obstet Gynecol, 2005. 192(5): p. 1752-8.

STUDY ENDPOINTS:

- 1. The primary study endpoint is to compare rates of SUI at 3 month post-operatively in patients who undergo laparoscopic sacrocolpopexy with and without Burch colposuspension. SUI will be defined by a composite outcome of: positive retro-fill cough stress test at 300mL, answer of "yes" to question #17 of Pelvic Floor Distress Inventory 20 (PFDI-20), or any treatment for SUI.
- 2. The secondary study endpoint is to compare complications, urinary symptoms, bowel symptoms, and sexual function in women with and without addition of laparoscopic Burch to sacrocolpopexy using the Pelvic Floor Distress Inventory 20 (PFDI-20) and Pelvic Organ Prolapse/Urinary Incontinence Sexual Questionnaire 12 (PISQ-12).

PROCEDURES INVOLVED:

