The retropubic space is exposed by dissecting the bladder and urethra posteriorly off of the pubic bone. Next, the area lateral to the urethra is cleared until anterior vaginal wall is identified. Non-absorbable monofilament suture (such as polytetrafluoroethylene or Gore-tex) is placed through Cooper's ligament, followed by a full thickness bite (excluding epithelium) of the anterior vaginal wall parallel to the urethra, and then back up through Cooper's ligament, so that the suture ends can be tied above the ligament. The location of each suture is as follows: a distal suture is placed approximately 2cm lateral to the proximal third of the urethra, and a proximal suture is placed 2cm lateral to the bladder wall at the level of the urethrovesical junction. This is repeated on the contralateral side for a total of 4 sutures. The sutures are tied down to form a suture bridge between the anterior vagina and Cooper's ligament, resulting in the gentle elevation of the anterior vaginal wall. Finally, the retropubic space is reperitonealized using delayed absorbable suture. (Walters and Karram, Urogynecology and Reconstructive Pelvic Surgery 2015).

As per standard operative protocol, cystourethroscopy will be performed on every patient at the conclusion of the surgery to evaluate for any bladder, urethral, or ureteral injury. No sham procedure will be performed in patients in the control group.

Participant Clinical Assessment: Participants will undergo standardized assessments at baseline and 3-months after surgery including demographics, past medical and surgical history, prolapse assessment using prolapse quantification system (POP-Q), retrofill cough stress test at 300mL, and completion of validated pelvic floor and sexual function symptom questionnaires including

Page 5 of 13 Version #: 2 Version Date: 10/6/20

Pelvic Floor Distress Inventory 20 (PFDI-20) and Pelvic Organ Prolapse/Urinary Incontinence Sexual Questionnaire 12 (PISQ-12).

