Safety Assessment and Follow up: Study participants will undergo established safety assessment and follow up protocols for post-operative patients. Participants will undergo standardized retrofill voiding trial in postoperative care unit (PACU) prior to hospital discharge to assess for voiding dysfunction. Patients with voiding dysfunction (defined as voiding less than 150mL following instillation of 300mL of sterile water) will be instructed to perform clean intermittent straight catheterization (CISC) or have indwelling Foley catheter placed based on patient preference and ability. An after-hours answering service is available for urgent patient questions and concerns. Participants will receive a standard follow-up phone call by office staff on post-operative day #1. Participants will have standard postoperative follow up appointments at 2 weeks and 3 months to assess for postoperative complications (urinary tract infection, voiding dysfunction, surgical site infection, mesh erosion).

No audio/video recordings will be utilized for this study.

	Pre-Op Visit	PACU	2 Week Post-	3 Month Post-
			Op ± 2 weeks	Op ± 4 weeks
Subject	Х			
Recruitment/Consenting				
Collection of	Х			
Clinical/Demographic				
Information				
POPQ Measurements	Х		X	X
PFDI-20	Х		X	Х
PISQ-12	X		X	Х
Empty Supine Stress	Х			
Test				
Surgical Procedure Form		Х		
Retrofill Voiding Trial		Х		
Assessment of Adverse			Х	Х
Events Form				
Retrofill Cough Stress				Х
Test at 300 mL				

DATA AND SPECIMEN BANKING

Data will be collected and stored at Northwestern Medicine. All study data will be recorded on Data Collection Forms by a research coordinator or study personnel and securely maintained in a locked cabinet that only study personnel have access to. Data will be entered by a research coordinator at Northwestern into a REDCap database that will be stored on a secure sever. Only

Version #: 2 Version Date: 10/6/20 Page 6 of 13 study staff will have passwords to access the project data on REDCap. All users of REDCap need an institutional username and password to log in and to enter data. Research personnel, including study staff as well as study doctors will be able to collect and have access to subject data.

After all data is collected, it will be downloaded from REDCap to Excel and SPSS and analyzed on Northwestern servers only and on computers that are Northwestern property and password protected by Northwestern.

SHARING RESULTS WITH PARTICIPANTS

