Participants may inquire about the individual measurements of their exam if desired. Patients can be unblinded after their 3 month visit. Study results may be given to patient at the completion of the study.

STUDY TIMELINES

An individual will participate in the study for a maximum of 4 months from the time of enrollment. Participants will be enrolled in the study at their preoperative visit and will be evaluated again in the postoperative recovery room, at the 2 week and 3 month post-operative visits.

We originally anticipated that it would take 24 months to enroll 50 patients however recruitment has taken longer. Adding an additional recruitment site will help us with our efforts. We anticipate recruitment will be completed December 2021 with analysis completed by June 2022.

	Months 1-12	Months 4-15	Months 15-16
Patient Enrollment	Χ		
Patient Follow-up		Х	
Period			
Data Analysis			Х

INCLUSION AND EXCLUSION CRITERIA

Inclusion Criteria

- Women over age 18
- English or Spanish speaking and reading
- Symptomatic pelvic organ prolapse with any compartment at or beyond the hymen

- Stress-continent, as defined as response of "no" to question 17 of PFDI-20: "Do you usually experience urine leakage related to coughing, sneezing, or laughing?", as well as a negative empty supine stress test.
- Planning laparoscopic or robotic sacrocolpopexy, with or without hysterectomy
- Have completed childbearing

Exclusion Criteria

- Adults unable to consent
- Pregnant women or patients desiring future pregnancy
- Patients undergoing uterine sparing surgery
- Individuals under age 18
- Prior procedure for stress urinary incontinence
- Prior retropubic surgery

VULNERABLE POPULATIONS

N/A

RECRUITMENT METHODS

This study will recruit patients who present to the Urogynecology Clinic at the Integrated Pelvic Health Program (IPHP), Lake Forest Hospital, and Central DuPage Hospital, at the time of their initial or follow up surgical consult appointment. Specifically, women without symptoms of SUI, defined as a negative answer in response to question #17 in the Pelvic Floor Distress Inventory (PFDI)-20 who are planning to undergo minimally invasive sacrocolpopexy for symptomatic POP at or beyond the hymen will be approached for recruitment. There will be no external advertising.

COMPENSATION FOR PARTICIPATION IN RESEARCH ACTIVITIES

Study participants will receive a \$100 gift card at the end of the study follow up period.

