Participants will be notified of their blinded treatment allocation at the end of the 3 month follow up period. They will be informed, upon request, the findings of the study once all data have been collected and analyzed.

WITHDRAWAL OF PARTICIPANTS

We do not foresee any participants needing to be withdrawn without their consent. Participants who withdraw from the study for any reason will continue to be followed as routine post-surgical patients.

RISKS TO PARTICIPANTS

Version #: 2 Version Date: 10/6/20 Page 8 of 13 Potential adverse events from Burch colposuspension include urinary tract infection, cystotomy, ureteral injury, and ureterovaginal fistula formation. In the CARE trial, the rates of adverse events were rare and similar in patients undergoing sacrocolpopexy with and without Burch colposuspension (4.5% and 3%, respectively). Patients randomized to the Burch colposuspension had longer operating room times (20 additional minutes) and increased blood loss (additional 73mL). The clinical impact of these factors is thought to be minimal.

There are no foreseeable psychological, social, legal, or economic risks to participants.

Patients undergoing sacrocolpopexy at our institution undergo concomitant hysterectomy, or have already had a hysterectomy in the past. Patients who desire uterine-sparing prolapse surgery will be excluded from this study. Therefore by design, this study will not pose any risk to an embryo or fetus.

POTENTIAL BENEFITS TO PARTICIPANTS

Our current standard of care for patients undergoing POP repair includes urodynamic testing. Per the study protocol, participants will not have to undergo urodynamic testing, thereby avoiding a potentially uncomfortable diagnostic test.

Potential benefits to participants randomized to receive Burch colposuspension include possible decreased risk of developing occult SUI following prolapse repair and therefore a lower probability of needing subsequent treatment.

DATA MANAGEMENT AND CONFIDENTIALITY

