The primary outcome measure is stress incontinence symptoms 3-months after surgery. In CARE, 34% of women randomized to open Burch and 57% of controls had stress urinary incontinence 3-months after surgery. Assuming addition of a minimally invasive Burch colposuspension to minimally invasive sacrocolpopexy will result in similar rates of stress urinary incontinence, a sample size of 42 (21 in each group) would demonstrate that addition of a Burch is superior to no Burch with a superiority margin 15%, 80% power and type 1 error of 5%. Assuming a 15% study dropout rate, a total of 50 patients will be recruited for this study.

Data will be collected at Northwestern Medicine. All study data will be recorded on Data Collection Forms by a research coordinator or other member of the study team and securely maintained in a locked cabinet to which only study personnel have access. Data will be entered by a research coordinator at Northwestern into a REDCap database that will be stored on a secure server. Only study staff will have passwords to access the project data on REDCap. All users of REDCap need an institutional username and password to log in and to enter data. Research personnel, including study staff as well as study doctors, will be able to collect and have access to subject data.

Version #: 2 Version Date: 10/6/20 Page 9 of 13

After all data is collected, it will be downloaded from REDCap to Excel and SPSS and analyzed on Northwestern servers only and on computers that are Northwestern property and password protected by Northwestern.

PROVISIONS TO MONITOR THE DATA TO ENSURE THE SAFETY OF PARTICIPANTS

Adverse events associated with Burch colposuspension in conjunction with sacrocolpopexy will be recorded, and will include events such as post-operative urinary retention requiring catheterization, post-operative urinary tract infection, and persistent urinary urgency.

Subjects will be monitored at each study visit for adverse events. An assessment of adverse events form will be completed and will be recorded into REDCap electronic data capture system. The PI will be notified of any adverse events, which will be resolved with the patient.

PROVISIONS TO PROTECT THE PRIVACY INTERESTS OF PARTICIPANTS

To protect privacy interests, the personal health information collected for research purposes will be collected from the subject's electronic medical record to limit the amount of people they interact with and provide personal information to.

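### Does the disagreement over a baseline 300 mL cough stress test call for a change to the plan?

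*Combined protocol and SAP*

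**What the plan says.** Two places under PROCEDURES INVOLVED, in the combined protocol and SAP, bear on this.

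- The Participant Clinical Assessment paragraph begins "Participants will undergo standardized assessments at baseline and 3-months after surgery including demographics". Its list continues through history and POP-Q to "retrofill cough stress test at 300mL, and completion of validated pelvic floor and sexual function symptom questionnaires", the last of these being the PFDI-20 and PISQ-12.
- The schedule of assessments, at the end of Safety Assessment and Follow up, has a row labelled "Retrofill Cough Stress" (Test at 300 mL) with one mark, in the 3-month column. A separate row, "Empty Supine Stress" (Test), has one mark, at the pre-operative visit.

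Three other sections give the context. The inclusion criteria define stress continence as a negative answer to PFDI-20 question 17 "as well as a negative empty supine stress test". STUDY ENDPOINTS states "The primary study endpoint is to compare rates of SUI at 3 month post-operatively", with a positive 300 mL test as one of three components. DATA MANAGEMENT AND CONFIDENTIALITY gives the planned size: "a total of 50 patients will be recruited for this study".

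**The concern.** The narrative is worded as an instruction, and the schedule contradicts it on whether a woman has her bladder filled to 300 mL and is asked to cough before surgery. The test is also a component of the primary endpoint, so doubt about when it is done deserves a check.

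If the narrative governs, a woman without the test has a missing baseline assessment. If the schedule governs, a woman who had it underwent something unscheduled. A statistician would also ask whether the presence or absence of a baseline result could bias the comparison of arms, change its precision, or alter what a positive 3-month test means.

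**Working it through.** **1. The narrative list against the schedule.** Demographics and history are both taken as the schedule's clinical/demographic information row.

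| Item in the narrative | Pre-op mark | 3-month mark |
|---|---|---|
| Demographics | yes | no |
| Medical and surgical history | yes | no |
| POP-Q | yes | yes |
| 300 mL cough stress test | no | yes |
| PFDI-20 | yes | yes |
| PISQ-12 | yes | yes |

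A literal reading needs 6 × 2 = 12 marks. The schedule has 5 + 4 = 9, so three items do not match and three do. The narrative also leaves out the empty supine test, which eligibility requires, and the POP-Q, PFDI-20 and PISQ-12 that the schedule marks at 2 weeks. The sentence pools items across two visits and is neither complete nor specific to a visit. The schedule is itemised, and its pre-operative stress test is the one the inclusion criteria name.

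**2. Where a baseline 300 mL result would be used.**

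- Eligibility: no. It rests on question 17 and the empty supine test.
- Allocation: no. The Randomization paragraph describes permuted blocks with equal probability and names no stratification factor.
- Primary endpoint: no. It is status at 3 months, not change from baseline.
- Planned analyses: none uses it.

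Allocation is released in the operating room on the day of surgery. A test at the pre-operative visit comes before it, so whether that test is done cannot depend on the arm.

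**3. Size.** The planned total follows from 42 evaluable women and 15% dropout: 42 / (1 − 0.15) = 49.4, rounded up to 50. Pre-operative 300 mL tests are therefore 0 (schedule) or up to 50 (narrative). The 3-month result is due for the same women on both readings, so the risk difference and its standard error do not change.

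**4. Could an unmeasured baseline result bias the comparison?** Randomization says no, and a simulation agrees. The BACKGROUND section gives the earlier open-surgery trial's 3-month rates as 57.4% (control) and 33.6% (Burch) overall, and 47.9% and 22.9% in women negative on preoperative urodynamics. Let f be the share of women positive at baseline. The documents do not give f for this trial, so 20% to 40% is assumed, with urodynamic status standing in for the 300 mL test. The implied control rate in positive women is

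c = [0.574 − (1 − f) × 0.479] / f,

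and the Burch rate follows in the same way from 0.336 and 0.229. With 21 women per arm, 400,000 simulated trials per setting and a pooled two-sided z-test:

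| f | c | Mean difference, no effect | Type I error | Mean difference, earlier trial's effect |
|---|---|---|---|---|
| 0.20 | 0.954 | 0.0001 | 0.049 | 0.238 |
| 0.30 | 0.796 | 0.0001 | 0.048 | 0.238 |
| 0.40 | 0.716 | 0.0002 | 0.049 | 0.238 |

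The last column matches 0.574 − 0.336 = 0.238. Leaving the baseline result unmeasured introduces no bias and does not inflate the error rate.

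**The case for a change.** The best case for acting is that the narrative is operative text, nothing in the protocol ranks the schedule above it, and of the three mismatched items only this one decides whether a woman undergoes a physical procedure. Recruitment covers several locations, so staff could follow different places in the document. The contradiction itself stands, but the divergence between sites is an inference. A protocol sets out a plan and would not be expected to show which instruction was followed.

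Two supporting arguments are weaker.

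- **Electronic consent.** Women who take the form home may consent online and have no further appointment before surgery, so a baseline test after consent might seem impossible for them. But CONSENT PROCESS mentions only surveys and appointments and does not exclude testing on the day of surgery. The schedule's own pre-operative POP-Q and empty supine test raise the same timing question.
- **Stated benefit.** POTENTIAL BENEFITS TO PARTICIPANTS says "participants will not have to undergo urodynamic testing, thereby avoiding a potentially uncomfortable diagnostic test". That concerns urodynamics. It gives no assurance against bladder filling, and on either reading women have a 300 mL instillation in the recovery unit and the 300 mL test at 3 months.

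A last argument concerns interpretation. Without a baseline result, a positive 3-month test cannot be shown to be new. Under the assumptions above, f × c / 0.574 puts 33% (f = 0.20) to 50% (f = 0.40) of control-arm events in women already positive before surgery. This is a fair remark about the chosen definition of stress continence, but it rests on an assumed f and a different test. The endpoint does not claim new onset, and the earlier trial's difference was similar overall (57.4 − 33.6 = 23.8 points) and in test-negative women (47.9 − 22.9 = 25.0 points). Tabulating events by baseline result, if one exists, would be a matter of preference. With 21 evaluable women per arm the cells would be small.

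**Conclusion.** The two places disagree, and the likeliest explanation is a summary sentence written without regard to visit. Whichever one is followed, the primary outcome is measured at the same time, in the same women and by the same definition. The effect on the primary risk difference and its standard error is nil. The operational difference is 0 against up to 50 pre-operative tests, and no result depends on it.

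This conclusion rests on the documents' own description of eligibility, allocation and endpoint, none of which uses a baseline 300 mL result. It does not depend on the assumed baseline positivity, which enters only the simulation and the remark on interpretation. The two places should read alike, and which instruction was meant is for the sponsor to say. That is editing, and it brings no gain in bias, precision, power or ability to answer the trial's question, so the plan needs no change on this point.

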PROTOCOL TITLE: MICRO (Minimally Invasive Burch Colposuspension to Reduce Occult Stress

Incontinence)

Clinical trial registration: NCT03841513

PRINCIPAL INVESTIGATOR:

Name: [name]

Department: Obstetrics and Gynecology, Division of Female Pelvic Medicine and Reconstructive

Surgery

[contact] Email Address: [contact]

CO-INVESTIGATORS:

Name: [name]

Department: Obstetrics and Gynecology, Division of Female Pelvic Medicine and Reconstructive

Surgery

[contact]

Email Address: [contact]

Name: [name]

Department: Obstetrics and Gynecology, Division of Female Pelvic Medicine and Reconstructive

Surgery

[contact]

Email Address: [contact]

VERSION NUMBER: 5 **VERSION DATE: 10/6/20**

STUDY SUMMARY:

Investigational Agent(s)	N/A
(Drugs or Devices)	
IND / IDE / HDE #	
Indicate Special Population(s)	☐ Children ☐ Children who are wards of the state ☐ Adults Unable to Consent ☐ Cognitively Impaired Adults ☐ Neonates of Uncertain Viability ☐ Pregnant Women ☐ Prisoners (or other detained/paroled individuals) ☐ Students/Employees
Sample Size	50
Funding Source	Northwestern Friends of Prentice Grants Initiative
Indicate the type of consent to be obtained	

Version #: 2 Version Date: 10/6/20 Page 1 of 13

	Waiver of HIPAA Authorization			
	Waiver/Alteration of Consent Process			
Cit	Lead Site (For A Multiple Site Research Study)			
Site	☐ Data Coordinating Center (DCC)			
Research Related Radiation	Yes			
Exposure	⊠ No			
DSMB / DMC / IDMC	Yes			
	⊠No			

OBJECTIVES:

Purpose: The purpose of this study is to examine surgical outcomes when prophylactic minimally-invasive laparoscopic (including robotic) Burch colposuspension is performed at the time of laparoscopic sacrocolpopexy.

Hypothesis: Stress-continent women undergoing laparoscopic sacrocolpopexy will have higher rates of occult stress urinary incontinence without the addition of the laparoscopic Burch colposuspension.

Specific Goals and Objectives:

Primary Objective:

1. To determine if addition of laparoscopic Burch colposuspension to planned laparoscopic sacrocolpopexy improves rates of stress urinary incontinence (SUI) in stress-continent women undergoing sacrocolpopexy for pelvic organ prolapse (POP). SUI will be defined by a composite outcome of: positive retro-fill cough stress test at 300mL, answer of "yes" to question #17 of Pelvic Floor Distress Inventory 20 (PFDI-20), or any treatment for SUI.

Secondary Objectives:

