Sacrocolpopexy is the gold standard surgical repair of pelvic organ prolapse of the apical compartment. The Burch colposuspension is a retropubic procedure in which the periurethral tissue of the anterior vagina is affixed to Cooper's ligament on either side using permanent suture bridges. In the Colpopexy and Urinary Reduction Efforts (CARE) trial [2] patients without preoperative symptoms of SUI were randomized to receive or not to receive concomitant prophylactic Burch colposuspension at the time of abdominal sacrocolpopexy. At three months, the subjects who underwent the Burch procedure were found to have lower rates of SUI after surgery (33.6%) compared to the control group (57.4%). Furthermore, of patients who tested negative for SUI on preoperative urodynamic testing, 22.9 % of those who underwent the Burch procedure had SUI compared to 47.9% in the control group. Burch colposuspension did not increase the rate of urinary retention, urge incontinence, urinary urgency, urinary tract infection, intra or post-operative complications. The data in this trial supported the placement of prophylactic Burch colposuspension at the time of abdominal sacrocolpopexy.

Over the last decade, there has been a shift away from open routes of surgical access secondary to decreased morbidity and quicker recovery associated with minimally invasive procedures. [4-7] As a result, open abdominal sacrocolpopexy with Burch colposuspension has fallen out of favor, and minimally invasive laparoscopic sacrocolpopexy is performed with greater frequency. Additionally, midurethral slings (MUS) have become the gold standard surgical procedure for the treatment of SUI and are performed more frequently than Burch colposuspension at the time of prolapse surgery. The Outcomes Following Vaginal Prolapse Repair and Midurethral Sling (OPUS) study [3] examined the placement of prophylactic MUS at the time of vaginal prolapse surgery. Patients with MUS had lower rates of SUI than control group at 3 months (23.6% vs 49.4%) and at 12 months (27.3% vs 43%). However, unlike the CARE trial, patients with concomitant anti-incontinence procedure had higher rates of adverse events including bladder perforation (6.7% vs 0%), UTI (31.0% vs 18.3%), major bleeding (3.1% vs 0%), and incomplete bladder emptying at 6 weeks (3.7% vs 0%). In addition, MUS carries the risk of mesh erosion into the vagina or urinary tract.

Version #: 2 Version Date: 10/6/20 Page 3 of 13

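### Does calling the primary outcome stress incontinence symptoms in the sample size paragraph create a second primary outcome?

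*Combined protocol and SAP*

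**What the plan says.** Two sections define the primary outcome, and they agree. The Primary Objective states: "SUI will be defined by a composite outcome of: positive retro-fill cough stress test at 300mL", and goes on to add a yes to PFDI-20 question 17 or any treatment for SUI. Study Endpoints, item 1, repeats the same three components and fixes the time: "The primary study endpoint is to compare rates of SUI at 3 month post-operatively".

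The sample size paragraph under Data Management and Confidentiality opens differently: "The primary outcome measure is stress incontinence symptoms 3-months after surgery". Its next sentence gives the planning rates: "34% of women randomized to open Burch and 57% of controls had stress urinary incontinence 3-months after surgery". The assumption that follows is again about rates of stress urinary incontinence. The Background reports the same cited trial as 33.6% against 57.4% SUI at three months.

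Recruitment Methods describes the women to be approached as "women without symptoms of SUI, defined as a negative answer in response to question #17" of the PFDI-20. In that section, therefore, symptoms means question 17 alone.

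**The concern.** Symptoms and the composite are different variables. A woman who leaks only on the cough stress test, or who was treated for SUI and is now dry, counts as an event under the composite but not under a symptom outcome. Recruitment Methods ties symptoms of SUI to question 17, so a literal reader could take the sample size paragraph to mean that item alone. That paragraph is the only statistical text in the document. No analysis section names the primary variable or test, and nothing says which wording governs.

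Two things would be at stake. First, a component cannot occur more often than its composite, so rates and power planned for SUI might not carry over to symptoms. Second, with two descriptions on record, a sponsor could call primary whichever gave the better result, which would raise the type I error.

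**Working it through.** **1. The plan's own figure.** Inputs from the sample size paragraph: 34% and 57%, margin 15%, power 80%, type 1 error 5%, dropout 15%. The stated number reproduces only when the margin is added to the 23-point benefit, at one-sided 5%:

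n per group = [0.34×0.66 + 0.57×0.43] × (1.645 + 0.842)² / (0.23 + 0.15)² = 0.4695 × 6.183 / 0.1444 = 20.1, so 21 per group and 42 in total. Then 42 / 0.85 = 49.4, so 50.

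Only one pair of rates enters, and the paragraph labels it stress urinary incontinence. Replacing the word symptoms with the composite changes no input, so 42 and 50 stand as written. Whether this form of calculation suits a superiority claim is a separate question and does not depend on how the outcome is named.

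**2. The wordings side by side.**

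| Place | Outcome named | Can it be computed as written? |
|---|---|---|
| Primary Objective | SUI, three-part composite | Yes |
| Study Endpoints, item 1 | SUI, same composite, 3 months | Yes |
| Sample size paragraph, first sentence | Stress incontinence symptoms, 3 months | No: no instrument, item or threshold |
| Sample size paragraph, next sentences | Stress urinary incontinence | By reference to the composite |

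**3. Power for a symptom-only outcome.** The documents give no symptom-only rates, so any figure is an assumption. For a two-sided 5% test at 21 per arm (normal approximation, unpooled variance):

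power = Φ( d / √{[p₁(1−p₁) + p₂(1−p₂)] / 21} − 1.96 )

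At 57% against 34%: 0.23 / √(0.4695/21) = 1.538, and Φ(1.538 − 1.96) = 33.7%. A pooled-variance version gives 32%.

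- *Assumption A: symptoms are the same fraction of composite events in both arms.* At 50%, 60%, 70% and 80%, power is 14.4%, 17.3%, 20.5% and 24.3%.
- *Assumption B: symptoms drop the same number of percentage points in both arms, so the 23-point difference stays.* 43% against 20% gives 38%; 33% against 10% gives 47%.

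Power falls under A and rises under B, and the documents do not choose between them.

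**4. Type I error from picking the better endpoint.** I simulated 400,000 null trials per setting: 21 per arm, composite rate 57% in both arms, symptoms 50% to 80% of composite events, success if either endpoint has p below 0.05.

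| Test | Composite alone | Either endpoint |
|---|---|---|
| Uncorrected chi-square | about 4.8% | 7.5% to 9.3% |
| Fisher's exact | about 2.0% | 3.3% to 4.0% |

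The documents name no test. A type I error above 5% is therefore a property of the chi-square assumption, and it also needs an analyst who sets aside two matching definitions.

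**The case for a change.** The strongest case for acting is that the mismatch is in the text, it concerns the outcome that decides the trial, and one sentence would remove it. Question 17 and the cough stress test are both collected at three months, so either outcome could be computed. The secondary urinary symptoms listed in the objectives do not include stress leakage, so the sample size paragraph is the only place where a stress symptom stands alone, and there it is called primary. Even with Fisher's exact test, free choice between two endpoints would nearly double the error rate, although it stays below 5%.

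Part of this stands. The wording is inconsistent, and a narrower reading is possible. The documents also do not say how SUI was defined for the 34% and 57%, so it cannot be shown that those rates belong to this composite. Equally, it cannot be shown that they were meant for symptoms, and the paragraph's own label points the other way.

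The step from an inconsistent phrase to two primary outcomes does not stand. A sample size paragraph that gives no measurement rule does not override the two sections whose purpose is to define the endpoint. Listing question 17 and the cough stress test as named secondary outcomes is a preference and is not needed to settle what is primary.

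**Conclusion.** This is a clerical looseness, and an analyst would resolve it correctly. The composite at three months is the only primary outcome that the documents define well enough to analyse, and the Objectives and Study Endpoints sections agree on it. Tidying the sentence would do no harm, but it would alter nothing that is done: 42 evaluable and 50 recruited patients, the same assessments and the same analysis.

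The suggested size of the harm cannot be established from the documents. Power for a symptom outcome ranges from 14% to 47% at 21 per arm, below or above the 34% for the planning rates, depending on an assumption about how symptoms relate to the composite in each arm. The type I error from selecting an endpoint ranges from 3.3% to 9.3%, depending on a test that the plan does not name. The conclusion rests on reading the paragraph's opening phrase with the sentences that follow it and with the two sections that define the endpoint. No change to the plan is called for.
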